2.2 Definition of analysis sets

Six analysis sets are defined below: all participant analysis set, full analysis set (FAS), safety analysis set, pharmacokinetic (PK) analysis set, extension period analysis set, and placebo-to-benralizumab extension analysis set. Participants must have provided their informed consent. If no signed informed consent is collected (important protocol deviation), then the participant will be excluded from all analysis sets defined below.

Note: "Enrolled" is defined as a participant's agreement to participate in a clinical study following completion of the informed consent process. "Randomized" participants are defined as those who undergo randomization and receive a randomization number. Potential participants who are screened for the purpose of determining eligibility for the study but are not randomized to the study will be considered "screen failures", unless otherwise specified by the protocol.

2.2.1 All participants analysis set

This analysis set comprises all participants who sign the informed consent form (ICF) for the study, and will be used for the reporting of disposition and screening failures.

2.2.2 Full analysis set

The FAS will comprise of all randomized participants who receive at least one dose of IP, irrespective of their protocol adherence and continued participation in the study.

Participants will be analyzed according to their randomized treatment irrespective of whether or not they were prematurely discontinued, according to the intent-to treat (ITT) principle. Data for participants who withdraw consent to participate in the study will be included up to the date of permanent discontinuation.

All efficacy data will be summarized and analyzed using an ITT approach based on the FAS. For consistency, demographic and baseline characteristics will be presented using the FAS.

2.2.3 Safety analysis set

The safety analysis set will comprise of all participants who receive at least one dose of IP. Participants will be classified according to the treatment they actually received.

Erroneously treated participants (eg, those randomized to treatment A but actually given treatment B) will be included in the group of the treatment they received. A participant who receives at least one dose of active IP will be classified as active and included in the active IP treatment group.

For the extension period, participants will be reported in their randomized treatment groups. Any deviations from the randomized treatment will be listed and considered when interpreting the safety data. These will not be identified until routine unblinding after the primary or final DBL.

All safety summaries and anti-drug antibodies (ADA) analyses will be based on the safety analysis set.

2.2.4 Pharmacokinetic analysis set

The PK analysis set will comprise of all participants who received benralizumab and from whom PK blood samples are assumed not to be affected by factors such as protocol deviations (eg, received wrong dose) and who had at least one quantifiable serum PK observation post first dose. A final list of protocol deviations that would lead to exclusion from this analysis set will be determined prior to DBL but may need to be updated post unblinding.

All PK summaries will be based on the PK analysis set.

2.2.5 Extension period analysis set

The extension period analysis set will comprise of all participants who start or carry on receiving at least one dose of benralizumab after the end of the Week 16 placebo-controlled

period, and thus entering the extension period. For the extension period, participants will be reported in their randomized treatment groups.

2.2.6 Placebo-to-benralizumab extension analysis set

All participants who received benralizumab at the start of the extension period who were previously randomized to placebo treatment will be included in this analysis set.

2.3 Violations and deviations

Participants who do not meet eligibility criteria but are still randomized and received at least one dose of IP will be analyzed according to the analysis sets described in Section 2.2. There is no intention to perform a per-protocol analysis in this study.

2.3.1 Important protocol deviations

Important protocol deviations are a subset of protocol deviations that may significantly impact the completeness, accuracy, and/or reliability of the study data or that may significantly affect a participant's rights, safety, or well-being.

The final list of important protocol deviations will be documented prior to unblinding the study data (primary DBL and final DBL) and may include but not be limited to the following categories:

- Eligibility criteria not met (participants incorrectly randomized)
 - Deviations from key inclusion criteria
 - Deviations from key exclusion criteria
- Deviations from informed consent procedures
- Discontinuation criteria for IP met but participant not withdrawn from IP
- Deviations from IP management and administration
- Received prohibited/restricted concomitant medication
- Other important protocol deviations
 - Scheduled study assessments not done or incorrectly performed which could impact the primary or key secondary endpoints
 - Unblinding of treatment assignment for reasons unrelated to participant safety
 - Other severe non-compliance (such deviations will be clearly described in the CSR).

Only important protocol deviations will be summarized and listed in the CSR.

Protocol deviations will be detected by means of on-site monitoring (observable protocol deviations) and programmatically derived important protocol deviations. The process for identification and assessment will be detailed in a separate protocol deviation plan.

2.3.2 Impact on analyses due to COVID-19 pandemic

Given the uncertainty surrounding the future impact of the COVID-19 worldwide pandemic on clinical trials, operational procedures are being implemented in this study to maintain the integrity of collected data. Efforts may be made to collect data via alternative means where possible, when on-site visits cannot be performed.

If there is a sufficient number of protocol deviations or study disruptions as a result of COVID-19, then sensitivity analyses will be conducted to evaluate their impact on the interpretation of results. Protocol deviations, including doses or visits missed due to COVID-19 related protocol deviations will be described separately in the CSR.

COVID-19 disruptions are broadly defined as follows:

- Changes to visit schedules, missed visits, changes to study procedures;
- Discontinuation of IP or changes to the IP supply;
- The introduction of alternative monitoring approaches.

Confirmed or suspected cases of COVID-19 will be listed and included as adverse events (AEs) as appropriate. This detail will form part of the protocol deviation plan.

3 PRIMARY AND SECONDARY VARIABLES

3.1 General definitions

3.1.1 Baseline definition

Generally, for efficacy data, the last recorded value on or prior to the date of randomization will serve as the baseline measurement. If time is collected, the assessment performed the same day but at a time prior to randomization will be included in the baseline definition. This includes both, the Week 16 primary and the Week 52 final analyses.

Generally, for safety data, the last recorded value on or prior to the date of the first dose of IP will serve as the baseline measurement. If time is collected, the assessment performed the same day but at a time prior to the first dose of IP will be included in the baseline definition. This includes both, the Week 16 primary and the Week 52 final analyses.

For the Peak Pruritus Numeric Rating Scale (NRS), the average of the daily scores for the 7 days prior to the day of randomization will be the baseline. If there is no value prior to the date of randomization, then the baseline value will not be imputed and will be set to missing. Further details on scoring the Peak Pruritus NRS will be provided in Section 3.3.2.

For PROs with recall periods of 1 week or more (POEM, DLQI/CDLQI, HADS, PGI-S, CCI EQ-5D-5L, SF-36v2), the time component of the definition of baseline (ie time of assessment relative to randomization) will not be considered; assessments on the same

day as randomization will be used to calculate baseline. If there is no assessment prior to randomization (or on the same day), then the baseline value will not be imputed and will be set to missing. Further details on scoring for PROs will be provided in Section 3.3.

When time of assessment is not recorded or missing, it is assumed that assessments recorded on the date of first dose of IP were performed prior to dosing, except in cases of protocol specified post-dose assessments. If there is no value prior to randomization (or the first dose of IP, depending on the endpoint), then the baseline value will not be imputed and will be set to missing. No data known to be collected post first dose will be used in determining the baseline value, unless otherwise specified.

For laboratory results and vital signs, baseline will be defined as the last non-missing assessment prior to first dose of IP. If no time is recorded for an assessment, and the assessment takes place at Visit 2, this will be assumed to be a pre-dose assessment. For physical examinations (complete or brief) baseline data will be collected at Visit 2 before first dose of IP.

Additional analyses for the participants who switch from placebo to benralizumab at Week 16 may be performed where the baseline value is set to the last recorded value prior to starting benralizumab (ie likely the Week 16 measurement) to obtain an assessment of the changes occurring while actually receiving benralizumab.

3.1.2 Change from baseline

Absolute change from baseline outcome variables are computed as:

$$(post\text{-}baseline\ value - baseline\ value).$$

Percent change from baseline outcome variables are computed as:

$$((post\text{-}baseline\ value - baseline\ value) / (baseline\ value)) * 100$$

If either the post-baseline value or the baseline value is missing, then both change from baseline and percent change from baseline value will also be set to missing. If the baseline value is zero, the percent change will be set to missing.

Calculations of change from Week 16 will follow the same approach.

3.1.3 Visit windows

For the Peak Pruritus NRS, weekly summary scores will be calculated using the 7 daily scores for each week, starting with randomization day (e.g. Days 1 to 7 for Week 1, Days 8 to 14 for Week 2), regardless of visit attendance days.

For Peak Pruritus NRS Week 16 score, the 7 days prior to the scheduled Week 16 timepoint (ie Days 106 to 112) will be used for calculation. However, only days prior to the first dose of IP in the extension period will be used for the Week 16 score derivation. If the Week 16 visit, and therefore the start of extension period IP dosing, occurs ahead of schedule (ie at Day 112 or earlier), then the 7 days prior to this day of first dose of extension period IP will be used for the Week 16 score, and the Week 15 score will be set to missing. If the Week 16 score cannot be calculated on the 7 daily scores, then an additional 1-day shift to assess the 8 daily scores before extension IP dose day will be assessed, and the Week 15 score will be set to missing. For Week 17 score, the scheduled 7 days before day 120 (ie Days 113-119) will be used. If the Week 16 visit occurs at Day 113 or later, Days 106 to 112 will be used in the Week 16 score as planned. Further details on scoring for daily Peak Pruritus NRS will be provided in Section 3.3.2.

For efficacy endpoints that present visit-based data, visit windows will be applied. The adjusted analysis-defined windows will be based on the collection schedule listed in the protocol and variables will be windowed to the closest scheduled visit for that variable.

Visit windows following baseline will be constructed in such a way that the upper limit of the interval falls halfway between two visits (the lower limit of the first post-baseline visit will be study day 2). If an even number of days exists between two consecutive visits, then the upper limit will be taken as the midpoint value minus 1 day. Visit windows are constructed so that every observation collected can be allocated to a particular visit. No visit windows will be defined for screening visits.

For assignment of data to adjusted analysis-defined visit windows, study day will be defined as follows:

$$(Date\ of\ assessment - date\ of\ randomization) + 1$$

Following this definition, for example if the day of randomization is study day 1 and date of assessment is the planned date of Visit 3 (Week 4), the study day will be 29 (28+1).

Any assessments performed after entering the extension period (ie the day after first dose of IP in the extension period at Week 16 visit) will be assigned to visit windows in the extension period and will not be assigned to visit windows in the 16-week placebo-controlled treatment period. Assessments at Week 16 visit will be assigned to Week 16.

If multiple assessments are recorded within a single adjusted visit window, please refer to the rules below:

- If there are 2 or more observations within the same visit window, then the non-missing observation closest to the scheduled study day will be used in the analysis.

- If 2 observations are equidistant from the scheduled study day, then the non-missing observation with the earlier collection date will be used in the analysis.
- If 2 observations are collected on the same day then the non-missing observation with the earlier collection time will be included in the analysis.

If a visit window does not contain any observations, then the data will remain missing.

For endpoints which are not collected at every visit (including PROs with recall periods of 1 week or more), the above rules will be applied to derive adjusted analysis-defined visit windows based on the protocol defined visit schedule for that endpoint.

Similarly, visit windows will be applied for laboratory parameters. Vital signs will be based on the case report form (CRF) visit designation.

When IP dosing needs to be postponed, it is recommended that all scheduled treatment visit procedures (except for IP administration) are still performed within the visit window. For further details see CSP Section 6.1.2.

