3.1.5 Intercurrent Events

Intercurrent events are withdrawal from the study at any time or requiring rescue therapy from Day 29 onwards. However, participants who started on placebo and switched to benralizumab in the extension phase are additionally permitted rescue therapy for 28 days from starting benralizumab, and thus additionally any rescue therapy use from Day 141 (ie 29 days after first dose of benralizumab) onwards will be considered as intercurrent event for these participants.

Withdrawal from the study will be considered from the day after withdrawal onwards, thus data on the day of withdrawal will be used as recorded. Rescue therapy from Day 29 (of first dose, and additionally for placebo-benralizumab participants from first benralizumab dose) onwards will be considered for intercurrent event imputation from the day of taking rescue medication onwards.

For responder or binary analyses, participants with intercurrent events will be considered as non-responders from the time these events occur. Participants with missing data for binary endpoints will also be considered non-responders at affected post baseline visits. Intercurrent events will be considered for analyses and descriptive summaries.

For change from baseline analyses or number and percentage of score category summaries, participants with intercurrent events will be considered as having missing scores from the time these events occur. Intercurrent events will be considered for analyses and descriptive summaries.

For summaries of number and percentage of individual questionnaire scores, all data will be presented as recorded, without imputation for intercurrent events.

The categorisation and imputations of responder status and reasons for non-response are provided in following table.

Table 3 Response Category Imputations

Response Category	Imputation Rule
Responder	Keep data as recorded, unless after taking rescue medication
Non responder	
Recorded as non-responder	Keep data as recorded, even if after taking rescue medication

Table 3 Response Category Imputations

Response Category	Imputation Rule
Missing	For missing questionnaire/visit, where participant remains in study and could be Responder or Recorded Non-responder or Rescue medication and remain in study
Rescue medication and remain in study	Impute if recorded as Responder and participant ongoing in study. Impute from day of rescue medication onwards, but only for assessments where participant is a Recorded Responder

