3.3.2 Peak Pruritus Numeric Rating Scale

The proportion of participants with an improvement of ≥ 4 points in peak pruritus weekly score at Week 16 will be used as the second key secondary efficacy variable.

The Peak Pruritus NRS is a one-item daily assessment of the worst itch the participant experienced over the past 24 hours. This is recorded every evening from Visit 1 onwards on the electronic device supplied to the participants. The score ranges from 0 to 10, with 0 being “no itch” and 10 being “worst itch imaginable.” and so a reduction in score is considered an improvement.

If a participant has at least 4 non-missing daily scores in a 7-day week, the peak pruritus weekly score is defined as the sum of the available daily scores divided by the number of days with non-missing daily scores. If there are less than 4 non-missing daily scores, then the weekly score is missing for that week.

The second key secondary endpoint is a binary response that will classify a participant as a responder if there is an improvement of 4 or more points in peak pruritus weekly score at Week 16 relative to baseline. Otherwise, participants will be classified as a non-responder.

In the statistical analyses, a binary variable will take on value 1 if a participant is defined as a responder, and value 0 for non-responder, and will be used as the response variable for the efficacy analysis.

The change from baseline in peak pruritus score at Week 2 will be analyzed as a secondary endpoint.

Intercurrent events will be considered as described above in Section Intercurrent Events (Section 3.1.5). Participants with a missing baseline score will have missing change from baseline status. Intercurrent events will be considered for analyses and descriptive summaries.

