4.1 General principles

The primary efficacy analyses will be based on the double-blind, 16-week placebo-controlled treatment period. Final analyses will be based on Week 52 end of study reporting. Efficacy endpoints will be analyzed using the FAS, the analysis of safety endpoints will be based on the safety analysis set. Analysis sets are defined in Section 2.2.

For the primary Week 16 analyses of binary endpoints, assessments after the use of rescue medication from Day 29 onwards will be considered as non-responders from the point of the rescue medication onwards. Any missing visits (including data after withdrawal of study at any time) will also be considered as non-responders, as described in Table 11 below.

For the primary Week 16 analyses of continuous repeated measures endpoints, any data after the use of rescue medication from Day 29 onwards or after withdrawal from study at any time will be treated as missing and the MMRM analyses fitted on the remaining available data.

For Week 52 analyses, for participants on benralizumab from randomization, rescue therapy use from Day 29 onwards will result in the participants being considered non-responders from the point of rescue use onwards. However, for participants who started on placebo and switched to benralizumab in the extension phase, rescue therapy users will only be considered as non-responders for the Week 52 analyses if it was taken from Day 141 (ie 29 days after first dose of benralizumab) onwards. Participants after withdrawal of study at any time will be considered as non-responders. Similarly, for change from baseline analyses, those intercurrent events will be considered as missing data.

Summary data will be presented in tabular format by treatment group. Categorical data will be summarized using frequencies and percentages, where the denominator for calculation is the underlying analysis set population unless otherwise stated. For efficacy reporting, the proportions of responders presented over time will include a number in analysis row to show the number of participants who have had the opportunity to reach each timepoint by the primary analysis based on their randomisation date, and this number in analysis will be used as the denominator for each visit.

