4.2.7.2 Proportion with improvement in peak pruritus numeric rating scale

The second key secondary endpoint of proportion of participants with an improvement of ≥ 4 points in peak pruritus weekly score at Week 16 for benralizumab 30 mg Q4W and placebo treatment groups will be analyzed using a logistic regression model in a similar way to that described for the primary endpoint analyses (Section 4.2.6.1).

The observed proportion of responders will be summarized using descriptive statistics by treatment group and each scheduled visit.

For the second key secondary endpoint, the null hypothesis is: the proportion of participants on benralizumab 30 mg Q4W is equal to the proportion of participants on placebo. Whereas, the alternative hypothesis is: the proportion of participants on benralizumab 30mg Q4W is not equal to the proportion of participants on placebo. That is,

$$H_0: \text{Difference in proportions (benralizumab 30 mg Q4W – placebo)} = 0$$

H_1 : Difference in proportions (benralizumab 30 mg Q4W – placebo) $\neq 0$

Sensitivity analyses for the key secondary endpoint may be considered if appropriate to explore the impact of rescue therapy use or missing data, respectively. Details are described above for the primary endpoint (Section 4.2.6.3).

The proportion of participants with improvement of ≥ 4 in peak pruritus weekly score at Week 52 will be analyzed as described above, comparing effects on the Q4W and Q8W maintenance regimens.

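### An early Week 16 visit blanks the Week 15 itch score, and the blank then counts as non-response in any weekly responder display

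*SAP*

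**What the plan says.** Section 3.1.3 builds weekly peak pruritus scores from consecutive seven-day blocks counted from randomization, whatever the visit dates. Week 16 is Days 106 to 112. Two rules can remove the Week 15 score:

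- If the Week 16 visit, and with it extension dosing, "occurs ahead of schedule (ie at Day 112 or earlier"), the seven days before the first extension dose "will be used for the Week 16 score, and the Week 15 score will be set to missing".
- If seven days do not yield a Week 16 score, "an additional 1-day shift to assess the 8 daily scores before extension IP dose day will be assessed", and Week 15 is again set to missing. Section 3.3.2 gives the minimum: "If there are less than 4 non-missing daily scores, then the weekly score is missing for that week".

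Missing binary data are then handled as follows:

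- Section 3.1.5: "Participants with missing data for binary endpoints will also be considered non-responders at affected post baseline visits". Its Table 3 lists a missing assessment as one of the non-responder categories.
- Section 4.1: "Any missing visits (including data after withdrawal of study at any time) will also be considered as non-responders". For responder proportions over time, it counts the participants who had the opportunity to reach each timepoint, and "this number in analysis will be used as the denominator for each visit".
- Section 4.2.7.2, on itch response: "The observed proportion of responders will be summarized using descriptive statistics by treatment group and each scheduled visit".

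No section exempts a score that the windowing rule itself has blanked.

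**The concern.** Each rule is defensible alone. Blanking Week 15 stops the same diary days from feeding two weekly scores. Counting missing data as non-response is a common conservative choice when the reason for missingness is unknown. Together they misfire: the Week 15 score is missing because of the date of a later visit, not because of itch, rescue or withdrawal. A participant who meets the 4-point criterion in Weeks 14, 15 and 16 but attends one day early is shown as responder, non-responder, responder.

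At stake is the time course of a key secondary endpoint. A dip one week before the tested timepoint could be read as loss of effect, and nothing in the SAP would warn the reader that the derivation caused it.

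**Working it through.** **Plan's own figures.** The SAP gives no Week 15 rate and no distribution of Week 16 visit dates, so there is no stated magnitude to reproduce. The windows can be reproduced. Week w covers Days 7(w - 1) + 1 to 7w. Week 16 is then Days 106 to 112 and Week 17 is Days 113 to 119, as Section 3.1.3 states. The same formula gives Week 14 as Days 92 to 98 and Week 15 as Days 99 to 105. The scheduled Week 16 visit is Day 113 (16 x 7 + 1).

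**How much of Week 15 is actually reused.** For first extension dosing on Day d (d at most 112), the shifted Week 16 window is Days d - 7 to d - 1.

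| Dosing day | Week 16 window | Days shared with 99-105 | Week 15 days left | At least 4 left? |
|---|---|---|---|---|
| 112 | 105-111 | 1 | 6 | yes |
| 111 | 104-110 | 2 | 5 | yes |
| 110 | 103-109 | 3 | 4 | yes |
| 109 | 102-108 | 4 | 3 | no |
| 108 | 101-107 | 5 | 2 | no |
| 107 | 100-106 | 6 | 1 | no |
| 106 | 99-105 | 7 | 0 | no |

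For visits one to three days early, the whole score is discarded although enough unshared days could remain under the 4-day rule. For visits on Days 106 to 109, a non-overlapping Week 15 score could not be formed anyway. The eight-day fallback, read literally, can blank Week 15 with no overlap at all: for dosing on Day 114, the eight preceding days are 106 to 113.

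**Effect on a displayed Week 15 rate.** Let p be the true Week 15 response rate and f the share of participants whose score is blanked, the same in both arms and unrelated to response. Blanked participants stay in the denominator and leave the numerator, so

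shown rate = p x (1 - f), and shown difference = true difference x (1 - f).

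For illustration, p is set to 40% and 10%. These are the planning rates in Section 1.2 for the IGA endpoint; the SAP gives none for itch.

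| f (assumed) | Benralizumab | Placebo | Difference (true: 30 points) |
|---|---|---|---|
| 5% | 38.0% | 9.5% | 28.5 |
| 10% | 36.0% | 9.0% | 27.0 |
| 20% | 32.0% | 8.0% | 24.0 |
| 30% | 28.0% | 7.0% | 21.0 |
| 50% | 20.0% | 5.0% | 15.0 |

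With 80 per group and f = 20%, the participants shown wrongly number 80 x 0.40 x 0.20 = 6.4 on benralizumab and 80 x 0.10 x 0.20 = 1.6 on placebo, at Week 15 only.

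**The case against.** The strongest objection is that no Week 15 responder display is specified. Section 4.2.7.2 speaks of scheduled visits, the non-response rule in 3.1.5 speaks of visits, and the dosing visits up to Week 16 are at Weeks 0, 4, 8, 12 and 16 (Section 1.1.2). If the itch summary is confined to site visits, the dip never appears. This stands as a condition on the point. It does not remove it: 3.1.3 derives a score for every week independently of attendance and writes explicit rules for Weeks 15 and 17, and change in itch at Week 2 is a secondary endpoint although the first post-baseline visit in the 3.1.3 example is at Week 4. Weekly reporting of itch is therefore implied, but not settled.

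A second objection is that an observed proportion means no imputation. Section 3.3.2 refers itch to 3.1.5 for analyses and descriptive summaries alike, and 4.1 fixes the denominator, so this reading does not hold.

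A third is that Table 3 separates missing from recorded non-response, so a dip could be traced if those categories are tabulated. That helps a careful reader, but the responder proportion is still wrong.

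Some stronger readings are tempting but not supported:

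- A reader might infer that everyone who attends early is misclassified. Only would-be responders change status; true non-responders and earlier rescue users are non-responders already.
- A reader might infer that the affected participants have complete diaries. The SAP does not say so, and the fallback applies only when fewer than 4 of 7 Week 16 days are available.
- A reader might infer a collapse in response. That needs a large f, and nothing in the SAP indicates its value.

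**Conclusion.** The point holds as a minor flaw in descriptive reporting. The rules as written make a Week 15 itch score missing because of visit timing and then count it as failure, so any weekly responder display understates Week 15 in both arms by the factor (1 - f). Its size cannot be fixed from the SAP. In the illustration, 40% and 10% become 38% and 9.5% at f = 5%, and 20% and 5% at f = 50%. This rests on three assumptions: Week 15 is displayed, f is equal across arms, and early attendance is unrelated to response.

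A reader might infer that the key secondary itch result is biased. It is not. The logistic models for itch response are planned for Weeks 16 and 52, and no Week 15 responder comparison is planned. The Week 16 test, the hierarchy in 4.1.1 and the Week 2 change endpoint are untouched by this rule. The continuous itch model treats a blank Week 15 score as missing, not as failure.

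**What to change.** Preferred: state in 3.1.5 that a Week 15 peak pruritus score blanked under 3.1.3 is excluded from both the Week 15 numerator and denominator and is not counted as non-response. Add the matching exception to the denominator rule in 4.1; without it the two sections would conflict.

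Alternative: score Week 15 from those of Days 99 to 105 not used for Week 16, under the existing 4-day rule, with the same exclusion when the overlap leaves fewer than 4 days. This keeps a score available for visits on Days 110 to 112 if the diary was filled in.

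Do not move the Week 15 window back to the seven days before the shifted Week 16 window. For a Day 112 visit that gives Days 98 to 104, which shares Day 98 with Week 14 (Days 92 to 98). For a Day 106 visit it gives Days 92 to 98, which is Week 14 itself. The double use would only move one week earlier.

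The cost is a sentence in 3.1.5, the exception in 4.1, a small programming change, and a slightly smaller Week 15 denominator, which a table footnote should explain. Section 4.2.7.2 could also say whether itch response is summarized by week or by site visit.
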